3.4 Exploratory Measures

Analyses of primary and secondary endpoints at other study intervals

The primary and secondary endpoints may be assessed at other study intervals not listed above.

Subject-shaded diagrams of pain

Subject-shaded diagrams are a common tool for the diagnosis of pain.

Clinician satisfaction survey

A sponsor-developed Clinician Satisfaction Survey will be administered. This survey will be administered to the site personnel primarily completing device programming at each site and includes questions pertaining to use of the Sprint system as well as the overall impression of the therapy. This survey will be administered at the conclusion of the study enrollment for that particular clinical center and may be administered sooner as needed.

3.5 Safety Endpoint

The primary safety endpoint is the occurrence of device related adverse events. All adverse events (AEs) that occur during the study will be documented. Specific details regarding any observed AE will be collected on an Adverse Event Form and will be followed to resolution. Adverse Events will be tabulated and summarized at the conclusion of the study.

4.0 DEVICE DESCRIPTION

4.1 Overview

During lead placement, test needles connected to either the Sprint Stimulator (Section 4.4), or the Sprint Test Stimulator (Section 4.7), may be used to apply electrical stimulation to peripheral nerves in the lower limb to determine appropriate electrode location and stimulation parameters.

Each subject will receive up to two leads, which will be connected to up to two Sprint stimulators (*i.e.*, one lead per stimulator).

The key components of the Sprint PNS System are shown in Figure 3 and include:

Non-sterile single use disposable components for use by a single subject

■ **Sprint Stimulator**

2. **Sprint Pad**

■ **Smartpatch Cable**

■ **Smartpatch Lead Connector Tape**

■ **Alligator Clip Cable**

■ **Sprint Stimulator Battery**

■ **Sprint Test Stimulator Battery**

■ **Sprint Belt**

Sterile, single-use disposable components for use on a single subject

■ **Smartpatch MicroLead™ and Introducer**

■ **Smartpatch Lead Connector and Wrench**

■ **Smartpatch Test Cable**

[figure not shown]
■ **Smartpatch Test Needle**

[figure not shown]
Non-sterile component for use by multiple subjects:

Sprint Test Stimulator

4.2 Smartpatch MicroLead™ and Introducer

4.3 Smartpatch Lead Connector, torque wrench, and Lead Connector Tape

[figure not shown]

4.4 Sprint Stimulator and Sprint Pad

[figure not shown]

4.5 Smartpatch Cable

4.6 Smartpatch Test Needle

4.7 Sprint Test Stimulator

[figure not shown]
[figure not shown]

Figure 9: Sprint Test Stimulator

[figure not shown]
4.8 Alligator Clip Cable

4.9 Smartpatch Test Cable

4.10 Battery

4.11 Sprint Belt

4.12 Accessories

5.0 SCOPE

5.1 NUMBER OF SITES

Up to 6 investigational sites.

5.2 NUMBER OF SUBJECTS

Up to 36 subjects will be enrolled in the study. Enrolled subjects are those that undergo procedures associated with lead placement. All enrolled subjects will receive a Subject ID number. The number of subjects to be enrolled does not include subjects who do not meet all of the eligibility criteria or who do not undergo procedures associated with lead placement.

6.0 STUDY PROTOCOL

6.1 Overview

This study is a prospective case series study to determine the treatment effect of Peripheral Nerve Stimulation (PNS) therapy for the treatment of knee pain following Total Knee Arthroplasty (TKA) utilizing preoperative lead placement.

6.2 Study Population

Prospective subjects will be screened for eligibility into the study from the available pool of candidates who are scheduled to undergo a primary unilateral TKA. Subjects will be screened using the Eligibility criteria listed in section 6.3. Recruitment materials will be provided to aid in subject enrollment. All recruitment materials will be IRB approved prior to their use.

6.3 Eligibility

6.3.1 Inclusion Criteria

1. At least 21 years old
2. Scheduled to undergo a primary unilateral total knee replacement procedure
3. Able to understand and willing to take part in study and comply with all study requirements

6.3.2 Exclusion Criteria

1. Body Mass Index (BMI) > 40 kg/m²
2. Compromised immune system based on medical history
3. History of valvular heart disease
4. Implanted cardiac pacemaker/defibrillator or Deep Brain Stimulator
5. Evidence of joint or overlying skin infection of the affected limb

6. History of recurrent skin infections
7. Bleeding disorder **OR** INR ≥ 1.5 for those on warfarin

Confounding conditions [REDACTED]

[REDACTED] History of nerve damage in the affected lower limb [REDACTED]

10. Allergy to skin surface electrodes and/or medical-grade adhesive tapes
11. Allergy to all local anesthetic agents such as lidocaine or previous reaction to anesthesia
12. Any other medical condition that may interfere with ability to participate in a clinical trial as determined by the Investigator
13. Prisoners, minors, legally incompetent people, unconscious patients, house staff, or students
14. Pregnant
15. History of substance abuse within 6 months

[REDACTED] Potential secondary gain issues [REDACTED]

6.4 Concurrent Medications and Non-Drug Therapies

Subjects will be permitted to use analgesic medications (opioid or non-opioid) as prescribed/recommended by their physician and analgesic usage will be recorded. For surgical anesthesia, subjects will not be allowed to receive any blocks in the upper thigh/buttocks (e.g., single injection or continuous blocks of the femoral or sciatic nerves) or blocks in any location using long lasting agents (e.g., liposomal Bupivacaine, or Exparel). Postoperatively, subjects will not be allowed to receive continuous regional nerve blocks. Subjects will also not be allowed to use other electrical stimulation therapies (e.g., transcutaneous electrical nerve stimulation [TENS] or neuromuscular electrical stimulation [NMES]) throughout the study. Additionally, any rehabilitation activities that may conflict with the device Instructions for Use (such as swimming or water therapy) should not be performed until after end of therapy. All interventions targeting pain control will be recorded on the appropriate pages of the Case Report Form (CRF).

6.5 Study Plan

The study procedures for this protocol are classified according to the following time periods: Consent; Lead Placement and Testing; Start of Treatment; In-Hospital Treatment; Post-Discharge Treatment; and Follow-up. Appendix A provides a schedule of the study procedures.

[REDACTED]

6.5.1 Visit 1 - Consent

Subjects will receive a detailed explanation of study specific procedures as well as the risks and benefits of participating in the study. The subject will be asked to sign the approved study consent during this visit. If the subject agrees to participate by signing the consent form, all inclusion/exclusion criteria will be verified by completing the eligibility form and then all baseline information will be collected and recorded on the appropriate case report form (CRF).

The subject's most recent pre-operative measurements of Range of Motion (ROM) may be documented, if available. The following outcome measures may be assessed:

- BPI-5 (“Average pain”) standard, at rest, and while walking
- Fixed Distance Walk test
- TUG test
- Six Minute Walk test
- BPI-9 (Pain Interference)
- WOMAC
- Pain Catastrophizing Scale (PCS)
- Current pain treatments and analgesic usage
- Assessment for opioid related side effects

[figure not shown]
If needed due to time constraints, any of the above outcome measures may instead be performed at Visit 2. Women of childbearing age will have a pregnancy test completed as part of eligibility confirmation before or at Visit 2.

[figure not shown]
[figure not shown]
6.5.2 Visit 2 – Lead Placement and Testing

[figure not shown]
[figure not shown]
Following the consent visit, participants who meet all eligibility criteria will undergo placement of the percutaneous Smartpatch MicroLeads. Visits 1 and 2 may be performed on the same day. As a safety precaution to prevent potential excessive bleeding, subjects on warfarin will have blood drawn to confirm an INR of < 1.5 . If the INR is not below 1.5, subjects will be given the opportunity to have their warfarin dosage adjusted and the INR will be retested up to two additional times. The INR must be collected within 48 hours prior to the Lead Placement and Testing (Visit 2).

[figure not shown]
The following outcome measures may be assessed prior to lead placement:

- Subject-shaded leg pain diagram
- Current pain treatments/analgesic usage
- Opioid-related side effects
- ROM (knee flexion and extension) and pain during ROM (pre-lead placement ROMs optional)

[figure not shown]

Determination of stimulation parameters:

Stimulus parameters will be varied over a range of parameters

Following lead placement, the following outcome measures may be assessed:

- ROM (knee flexion and extension) and pain during ROM
- Subject-shaded diagram of paresthesia coverage of leg

This study has a large number of stimulus parameters and ranges to investigate. It is possible that the optimal stimulus parameters may not be determined during this Visit. Thus, at the conclusion of this Visit a subject will

a. Proceed to treatment phase:

(i) Subjects with acceptable lead placement and stimulation parameters will be prepared to proceed to the treatment phase. Stimulation may be delivered up to the time of the TKA, provided the lead placement occurs more than 2 days prior to the TKA. The subject will be educated on the use of the system as noted in Section 6.6.3. Subjects receiving preoperative stimulation may complete the daily diary on each day stimulation is received as well as the PGIC and WOMAC on the last day of the diary.

[REDACTED]. Prior to surgery, the Lead Connector will be disconnected from the Smartpatch Cable and stimulator. The lead and lead connector will be secured beneath sterile, waterproof bandages (Tegaderm by 3M, Nexcare, or equivalent) and worn until completion of the TKA surgery. Following TKA, all subjects will use the stimulation system to determine if stimulation can provide pain relief. OR

b. Return for another Visit 2:

(i) If there is not sufficient time to complete lead placement or the testing, or if the subject does not respond to stimulation, the investigator may present the subject with the option to return for a repeat lead placement visit OR

c. Terminate from the Study:

(i) If the subject does not wish to continue with further lead placement, they will be terminated from the study if no adverse events (AE) are noted at a 24-48 hour telephone follow-up. If an AE is noted, the subject will be followed until the AE resolves.

Additionally, the site must ensure the subject does not have the lead for greater than 60 days (*i.e.*, if the subject received the lead 14 days prior to TKA, the site must schedule their End of Treatment visit so it is no later than 60 days after lead placement).

Data regarding the specific details of the lead placement procedure will be collected during this visit and recorded on the appropriate Case Report Form. Images (*e.g.*, photographic, video, ultrasound) may be collected to provide a visual record of the locations of electrodes/leads and anatomy. Subject consent will be obtained for photography or video recording, and subjects will be de-identified in photos or videos.

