6.5.3 Telephone Follow-Up (Visit 3)

All subjects will receive a Telephone Follow-up 24 - 48 hours after each Visit 2 (Lead Placement) to query for any adverse events. All AEs will be followed until resolution. Subjects

who return for Visit 2 but do not undergo lead placement will not receive a follow-up phone call to assess adverse events because they will not have participated in the lead placement procedure.

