11.2 Known and Anticipated Risks

The risks listed below are described as common ([REDACTED]), uncommon ([REDACTED]), or rare ([REDACTED]).

1) Risks associated with insertion of the needle introducer for lead placement

2) Risk of nerve damage from the needle or lead.

[figure not shown]

3) Risk of skin irritation, infection, or inflammation at the lead exit site

[figure not shown]
[REDACTED]

4) Risk of the percutaneous lead breaking beneath the skin

[REDACTED]

[figure not shown]
5) Risks associated with retained Percutaneous Lead fragments

A large rectangular area of the page has been completely blacked out, indicating that the content has been redacted.

6) Risks associated with lead fragment removal

[figure not shown]
7) Risk of lead replacement

[figure not shown]
8) Risk of skin irritation under the Sprint pad, Smartpatch lead connector tape, bandages, or belt

[figure not shown]
9) Risk of mechanical or electrical failure of the Sprint stimulator

10) Risks for pregnant women

11) Risk of discomfort or increased pain

12) Risk of worsening of pain symptoms

13) Risk of tissue damage

14) Risk of falls

15) Risks associated with Diathermy

16) Risks associated with MRI

17) Risk of allergic reaction to local anesthetics (if applicable)

18) Risk associated with venipuncture (if applicable)

19) Risk associated with conscious sedation (if applicable)

20) Risk of loss of confidentiality

21) Risk of swallowing or choking on battery

[figure not shown]

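### Enrolled subjects who decline further lead placement and report no adverse event at the 24-48 hour call have no later safety contact, so late device-related events in this group could go uncounted

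*Combined protocol and SAP*

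**What the plan says.** Section 5.2 defines enrolment by exposure to the procedure: "Enrolled subjects are those that undergo procedures associated with lead placement". The ceiling is 36 subjects. Section 7.1 draws the same line from the other side: those who consent but do not go on to these procedures, or who fail eligibility, are screen failures.

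Section 6.5.2 gives three outcomes of Visit 2: proceed to treatment, return for another Visit 2, or leave. The third applies narrowly: "If the subject does not wish to continue with further lead placement". For those subjects, "they will be terminated from the study if no adverse events (AE) are noted at a 24-48 hour telephone follow-up". There is a safeguard: "If an AE is noted, the subject will be followed until the AE resolves".

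Section 6.5.3 provides a call after each Visit 2, but subjects who return for Visit 2 and "do not undergo lead placement will not receive a follow-up phone call to assess adverse events". The reason given is that they took no part in the procedure.

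Section 3.5 states: "The primary safety endpoint is the occurrence of device related adverse events". It documents events arising during the study. Section 8.3 says events will be documented, reported and categorised, but names no safety set, denominator or observation window. Subjects who continue are asked about adverse events up to the 3-month visit after knee replacement (section 6.5.8).

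**The concern.** A subject who leaves under option (c) is enrolled and has been exposed to the invasive step. If the call finds nothing, the study asks that subject nothing further. Section 11.2 lists risks that belong to that step, including "Risk of nerve damage from the needle or lead", exit-site infection or inflammation and, where a lead was inserted, retained fragments. Nothing visible says these would all declare themselves within 48 hours.

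The exits are also unlikely to be a random sample. Option (c) sits beside the option of a repeat visit, which is offered when placement or testing could not be completed or the subject did not respond to stimulation. Leavers are therefore likely to include the unsuccessful placements, which a feasibility study particularly needs to describe.

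Two uses of the data depend on the count. Section 8.3 intends the results to refine consent forms and the risk-benefit profile for future studies. Section 10.0 reclassifies an anticipated device effect as unanticipated when it is more frequent than expected. With at most 36 subjects, one or two unrecorded events could change either reading.

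**Working it through.** The plan gives no figure to reproduce: it states no adverse event rate, early-exit rate or precision target for safety. The check is mainly textual, with an illustration of scale.

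**Step 1. Does the gap follow from the text?**

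1. The subject had lead-placement procedures, so is enrolled and not a screen failure (5.2, 7.1).
2. The subject declines further placement and reports nothing at the call after the last Visit 2, so is terminated (6.5.2(c), 6.5.3).
3. Events are captured while the subject is in the study (3.5), so planned capture stops at termination.
4. No later contact for this subject appears in sections 6.5.4 to 6.5.9 or in the readable part of Appendix A.

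An event that starts after the call would reach the data only if the subject volunteered it and the site chose to record it.

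**Step 2. Length of observation.**

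- Option (c), no event at the call: 1 to 2 days after the last Visit 2.
- Continuing subject: 3 months after surgery, about 3 × 30 = 90 days, plus up to 14 days from lead placement to surgery, so 90 to 104 days.
- Ratio: from 1/104 = 1.0% to 2/90 = 2.2%.

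This measures unequal observation. It does not measure events missed, because exposure differs too.

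**Step 3. Scale, on assumed inputs only.** Let k be the number of option (c) exits with no event at the call, and q the chance that such a subject has a first device-related event afterwards. Neither is in the documents. I take k = 1 to 6 and q = 2% to 20%.

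Expected subjects missed = k × q. Chance of missing at least one = 1 − (1 − q)^k.

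| k | q | Expected missed | Chance of at least one |
|---|---|---|---|
| 0 | any | 0 | 0 |
| 1 | 2% | 1 × 0.02 = 0.02 | 2% |
| 2 | 5% | 2 × 0.05 = 0.10 | 1 − 0.95² = 10% |
| 4 | 10% | 4 × 0.10 = 0.40 | 1 − 0.90⁴ = 34% |
| 6 | 20% | 6 × 0.20 = 1.2 | 1 − 0.80⁶ = 74% |

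If all 36 stayed in the denominator and late risk were the same in everyone, the late-event proportion would be understated by k/36 in relative terms: 1/36 = 2.8%, 2/36 = 5.6%, 4/36 = 11.1%, 6/36 = 16.7%. Equal risk probably overstates this, since leavers do not have weeks of indwelling lead and stimulation.

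**The case against.** The strongest reply is that nothing shows any harm will be missed. A reader might infer that the endpoint is undercounted as a matter of fact. The documents do not support that: they give no exit count and no late-event rate, and if nobody leaves this way the effect is zero. Nor is there a defined adverse event rate to be biased, because section 8.3 sets no denominator or window. This stands, and it limits the point to what could happen.

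The rule is also less abrupt than it may look. A repeat Visit 2 brings a further call, and an event noted at a call is followed to resolution. Both are true, but neither reaches an event that begins after the last call.

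A reader might take the contrast of about 104 days with 2 as the size of the problem. It is not. Continuing subjects may carry leads for up to 60 days and receive stimulation for much of the day, so part of the difference in follow-up matches a difference in exposure.

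A reader might also infer that section 6.5.3 contradicts 6.5.2(c) by denying the call to subjects who had only a test needle. That reading is weak. Section 4.1 places test needles within lead placement, and the reason given in 6.5.3 covers only people who took no part in the procedure. Read together, a needle-tested subject should be called. The wording could be clearer, but it is not a firm conflict.

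Finally, text around Visit 2, the detail of the risks in 11.2, and an Appendix A footnote attached to the follow-up call are redacted or missing. They could bear on this point, so the conclusion is confined to the visible text.

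**Conclusion.** The point holds in a limited form. On the visible text, enrolled subjects who decline further lead placement and report no adverse event at the call after their last Visit 2 have no later safety contact. Device-related events that begin afterwards could be absent from the primary safety endpoint, and section 8.3 does not say how such subjects are handled.

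The documents do not allow the amount to be computed. The illustration runs from 0.02 to 1.2 expected subjects and rests wholly on the assumed k and q. It does not establish that an undercount will occur, or that any listed risk appears late in people who never received treatment. The gap does not undermine the study, but it concerns the primary safety endpoint and is cheap to close, so it should be dealt with.

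**What to change.** 1. **Section 6.5.2(c).** Leave unchanged the subject's decision to stop and the end of efficacy assessment. Instead of ending safety observation at the 24-48 hour call, keep these subjects, with their consent, in brief telephone follow-up for adverse events only. Where possible, time it to contacts the plan already has. The 2-month contact is suitable, since section 6.5.8 already allows it by telephone. The 2-week and 3-month contacts are in-person visits, so calls at those times would be new, as would a separate call before surgery.
2. **Sections 5.2, 6.5.2(c) and 6.5.3.** Reconcile the wording so that anyone who had a test needle or lead inserted clearly receives the 24-48 hour call.
3. **Section 8.3.** Tabulate device-related events for all enrolled subjects. Show those terminated at Visit 2 separately, with their number and length of follow-up, so that unequal observation is visible.

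The cost is a wording change, a sentence in the consent form and a few calls for each subject who leaves. Some will decline the calls. Events after knee replacement may be hard to attribute to the device or to the surgery, which is a further reason to report this group separately. The recorded event count may rise slightly.

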6.5.3 Telephone Follow-Up (Visit 3)

All subjects will receive a Telephone Follow-up 24 - 48 hours after each Visit 2 (Lead Placement) to query for any adverse events. All AEs will be followed until resolution. Subjects

who return for Visit 2 but do not undergo lead placement will not receive a follow-up phone call to assess adverse events because they will not have participated in the lead placement procedure.

6.5.4 Day of TKA and Start of Stimulation following TKA (Visit 4)

Following TKA surgery, the bandages covering the leads will be carefully removed and the leads will be connected to the Stimulators. Stimulation will be delivered to determine if postoperative pain can be reduced. [REDACTED]

[REDACTED] Stimulation will be delivered for up to approximately 24 hours/day (except when bathing, changing the battery, etc.) until end of therapy (*i.e.*, approximately 6 weeks following TKA surgery. Leads will be indwelling for no more than 60 days total). Additionally, Visits 1, 2 and 4 may occur on the same day, such as the day of the TKA (if so, visit 3 is not required).

Stimulation parameters may be varied. [REDACTED]

[REDACTED] The care and maintenance of the stimulation system, leads, and lead exit sites will be performed by members of the clinical or study staff. Subjects will also be provided with a manual and instructed on the use and care of the device in case changes are required when clinical/study staff is not present.

Sterile, waterproof covering bandages [REDACTED] will be placed over the exit sites of the leads. Additional bandages may secure the lead connections. The site may choose to utilize a skin adhesive [REDACTED] The clinical/study staff and subject will be instructed to inspect the electrode exit site for signs of irritation and report them to the clinician. [REDACTED]

[REDACTED] The area around the leads and surface electrodes will be kept clean and dry. If bandages become wet or loose, the bandages will be changed. A bandage change will not be considered an Adverse Event (AE), but may be documented.

The following outcome measures may be assessed during Visit 3:

- Patient shaded leg diagrams of pain [REDACTED]
- Current pain treatments/analgesic usage
- Subjects will be given a diary to record their daily “Average Pain” [REDACTED] The diary will be completed for each day of treatment.

